### C. Study Design and Research Methods

We propose an open-label, pilot feasibility trial (n=45-60), randomizing hospitalized patients to receive XR naltrexone, IV ketamine, or neither prior to hospital discharge, along with enhanced linkage to care. The primary clinical

outcome compared across each of the groups will be 30-day re-admission rates ascertained by chart review (Table 1).

To reduce variability, all participants will undergo a standard addiction consultation that includes behavioral components such as supportive therapy and motivational interviewing. They will also receive enhanced linkage to care (hereon “linkage”) which includes being met by a staff member while in the hospital to begin the clinic intake process and assign a follow-up appointment date. Linkage will also include a contingency management (monetary incentive to follow-up) in their post-hospital transition and receive standard case management and counseling at Substance Use Disorder Services (SUDS) clinic.

ACS team members will identify patients meeting inclusion criteria (Table 2), and – after conducting their usual consultation – approach them about the study. Approximately 900 patients met similar inclusion criteria in 2019 (Query by [name]). After screening for exclusion criteria, informed consent will occur, and initial baseline data will be obtained by “Treatment on Demand” (TOD), a grant-funded team of counselors who are already linking hospitalized patients to addiction care. Consented patients will then be randomized, and the ACS will work with the primary team to order and administer the assigned intervention close to discharge. Meanwhile, a TOD counselor will work to establish a follow-up date within seven days post-discharge. Additional data will be collected immediately after the intervention (for those in one of the two medication groups), at SUDS follow up, and 30-days post-discharge by chart review.

### ***Medications***

XR naltrexone is produced by Alkermes. Due to the cost (~\$1300 on GoodRx for one dose), we will receive samples from Alkermes in a process that has been pre-arranged between DH inpatient pharmacy and their Colorado-based representative, [name]. We received preliminary approval on 12/3/19 from DH Pharmaceuticals and Therapeutics Committee to use these samples in the hospital for this purpose.

IV ketamine is currently utilized at DH at sub-anesthetic doses for pain control, with guidance from PolicyStat #5253340. Its use in pain management is currently limited to ICU settings and utilizes boluses and infusions titrated to pain. According to discussions with inpatient pharmacy, approval for an infusion dose modeled after randomized trials may be granted for use on floor units with specific contingencies: physician/investigator will be present at bedside during the infusion and nursing staff are educated on the protocol. This was discussed at Denver Health’s Medication Administration Forum (MAF) meeting on 3/5/20.

### ***Data Collection***

Data will be primarily collected at four time-points (Table 4). Data will be entered by staff into a REDCap database on tablet computers in the hospital and at SUDS clinic. Data collected at enrollment will primarily be descriptive, including demographics, recent drinking history, readiness to change, and various contributing factors to drinking. Immediately after intervention, vital signs,

symptoms, and acceptability will be recorded. Data collected on post-discharge arrival to SUDS clinic will include most 2' clinical outcomes. We will obtain re-admission rate (1' clinical outcome) through chart review, conducted by research team members at 30-days post-discharge.

Table 4 Patient flow and data collection points

Step	Who	Notes	Data collected – staff entered
Patient identified on consult list	ACS	Quick screen that meets inclusion criteria	
↓			
Addiction consult performed	ACS	Evaluation, withdrawal management, medication (though if patient consents to study, will not be prescribed an addiction medication at discharge), brief therapy, referrals, disease screening/harm reduction	
↓			
Screen, consent, randomization	ACS	Formal screen to identify any exclusion criteria. Simple randomization by algorithm	
 
• E-Consent (should include consent to see records in “care everywhere” – some hospitals require permission – when checking for ED visits and re-admissions)
 
• Screening documentation (inclusion and exclusion criteria)
 
• Alcohol-related admissions in last 12 months (date, location, top 3 diagnoses)
 
• Assigned group
 

↓			
Baseline data, referral to SUDS [data collection point #1]	ToD	ToD collects baseline data first, then performs “biopsychosocial intake” and sets up SUDS appointment within 1 week of discharge.  Discharge date is not always predictable;	
 
• Demographics
 
• Baseline clinical data
 
• Depression symptoms baseline (PHQ9 2 wks)
 
• Drinking History 7-days prior to admission (TLFB)
 
• Readiness to change (SOCRATES-8A)
 
• ACE Questionnaire
 

		ACS to review active hospitalized research participants and contact ToD/update date in RedCap as needed.	
↓			
Intervention administered [data collection point #2]	RN, ACS	
For 'linkage-alone' group, data to be entered following consult.
 
For NTX group, intervention administered prior to discharge (could be same day as consent). Vitals immediately preceding and 40 min post- injection. Data collected after administration.
 
For KET group, intervention administered prior to discharge (could be same day as consent), though should have no food for at least 3 hours (~50% gastric emptying). Vitals immediately preceding, after completion, and 2 hours following end of intervention.
	
 
Vital signs (HR, BP, O2): linkage-alone group- baseline only, recorded after consult. NTX group- baseline, 40 min after administration. KET group- baseline, end of administration (~40min), 2 hours after end of administration.
 
Most recent AST, ALT
 
UDS-5 data
 
[for KET] Dissociative symptoms (CADSS) after administration (40 min)
 
[for NTX and KET] Acceptability of intervention (10-point Likert) after administration
 
[for NTX and KET] Readiness to change (SOCRATES-8A) after administration (40 min)
 
 
ORDER: CMP (if not already obtained), UDS-5 (if not already obtained)
 
ORDER in discharge orders (outpatient): CMP, UDS-5, urine EtG (if not already ordered)

↓			
Presentation to SUDS, data entered, contingency management reward administered [data collection point #3]	SUDS staff	
Upon presentation, staff to collect study data. After completion, will receive contingency management reward.
 
Then patient to complete standard intake/follow-up visit, if willing.
	
 
Drinking History since discharge (TLFB since discharge)
 
Depression symptoms (PHQ9 modified to read "since discharge.")
 
Readiness to change (SOCRATES-8A)
 
[for KET] Dissociative symptoms (CADSS)
 
Adverse Events (Modified PRISE)
 
Acceptability of intervention (10-point Likert)
 

		Staff to instruct patient to present to the clinic laboratory (e.g. pav G) for CMP after the visit.	
 
Contingency management feedback (10-point Likert, open ended)
 

30-day chart review [data collection point #4]	Research staff	Should check encounters tab as well as “care everywhere” for Denver Metro region.	
 
Admissions (up to 5) within 30 days of discharge date (date, location, up to top 3 main diagnoses based on documentation available).
 
ED visits (up to 5) within 30 days of discharge date (date, location, up to top 3 main diagnoses based on documentation available).
 
AST, ALT obtained at SUDS f/u (if available)
 
Urine EtG obtained at SUDS f/u (if available)
 

Screening: The addiction consult team will attempt to screen patients meeting the inclusion criteria during inpatient admission. We anticipate 10 patients will meet inclusion criteria weekly. They will be assessed for clear exclusion criteria documented in the chart, and if none are noted the patient will be asked if they would like to join the study and complete the screening. If still no exclusion criteria are met and the patient expresses interest, they will be engaged in informed consent. The primary team will be notified by the addiction medicine team. Each combined process of screening and consent is anticipated to require 15 minutes at the end of a typical consultation. The screening window is anticipated to last 5 months.

Randomization: Patients will undergo a simple randomization algorithm to one of three arms.

Intervention:

- **Arm 1:** Receive a single dose of XR naltrexone (380mg) prior to discharge.
- **Arm 2:** Receive a single infusion of IV ketamine (0.5 mg/kg over 40 minutes) prior to discharge.
- **Arm 3:** No single-dose medication
- *All groups will receive enhanced linkage to care that includes contingency management, initiation of biopsychosocial intake, and appointment scheduling. This aspect alone surpasses the current standard of care.*

Contingency Management: Patients will receive a debit card prior to discharge from the hospital. We will utilize a pre-existing system - ClinCard by Greenphire. Participants will receive \$10 upon completion of baseline data, and \$20 upon completion of follow-up data (at SUDS clinic).

Follow up: Patients will be assigned a follow-up within 7 days of discharge at the outpatient addiction clinic (Denver Health SUDS clinic in pavilion K).

Standard of care: Current standard of care for alcohol use disorder in the hospital includes offer of medications (usually oral naltrexone) and addiction medicine consultation which can result in brief counseling and referral to SUDS clinic or other treatment program.

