#### **E. Potential Scientific Problems:**

One potential limitation is the small sample size. As a pilot study, our main aim is to test feasibility. A more robust, precise demonstration of clinical effectiveness will be pursued in a future project with data used from this study to inform sample size estimates as well as timelines.

Secondly, patients may be re-admitted to hospitals that do not show up in our medical record system (Epic). Insurance claims data would be ideal, but at this stage the added value does not justify the costs required for acquisition. Notably, Epic “Care Everywhere” can detect admissions in the University of Colorado Health system (12 hospitals in Colorado), SCL Health (5), and Centura Health (17). This network of hospitals provides high coverage based on our population, many of whom are homeless and located in a small regional geography.

Another potential limitation is a low follow-up rate at SUDS. This is one major reason for including contingency management as part of our enhanced linkage to care. Regardless, the primary quantitative outcome (hospital re-admission) will not require data from SUDS attendance to measure.

Alternative designs were considered but deemed beyond the scope of this proposal:

- “*Double dummy*” *placebos*, which can minimize bias in both researcher and participant. However, this would be personnel and time-intensive, and due to ketamine’s unique psychoactive effect, patients are unlikely to be successfully blinded.
- *2x2 factorial design*, which could gain information on combinations of multiple interventions, but would unnecessarily weaken inferences and complicate statistical analysis due to interactions in this small sample.
- *30-day in-person evaluation*, which would facilitate additional longitudinal measurement. However, we are not confident that enough patients would show up (or be reachable by telephone) to allow for meaningful analysis.

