#### **F. Data Analysis Plan:**

Participants’ demographic and baseline clinical data will be tabulated, and differences between groups will be assessed using a Fisher’s Exact Test for categorical variables and a two-sample t-test for continuous variables. These tests

will help evaluate the effectiveness of randomization. Feasibility outcomes (Aim 1) such as adverse events and acceptability (Likert scale) will be compared for each group using a Fisher's Exact Test and Wilcoxon-Mann-Whitney Test, respectively. Overall recruitment rate and follow-up rate will be tallied at the conclusion of data collection.

For Aim 2, all-cause hospital re-admission within 30-days of discharge will be recorded as a binary outcome. Rates of the two medication intervention groups (XR naltrexone or IV ketamine) will be compared against the group that received enhanced linkage to care alone.

This pilot study may not be sufficiently powered for robust hypothesis testing. By one crude estimate, we could have approximately 80% power to detect a difference between a medication group and the linkage-alone group with about 60 participants assuming a re-admission rate is 25% vs 15%. A larger effect size would increase our power and/or reduce the number of participants required. Regardless, this will provide parameter estimates that can inform a future sample size calculation in a larger effectiveness trial.

For further descriptive purposes, a secondary utilization outcome is risk of 30-day all-cause ED visits. This will be evaluated in a similar manner as hospital re-admissions. Additionally, we are interested in the within-subject difference in readiness-to-change. For those who follow-up, a mean of pre/post differences will be calculated, and a paired t-test will be used to determine if the null hypothesis ( $H_0$ : difference = 0) can be rejected. Drinking behavior will be measured using the Timeline Follow Back method. Binge drinking will be defined as 5+ drinks for men, 4+ for women, and the proportion of binge drinking days since discharge will be calculated for each group. Proportions of positive urine ethyl glucuronide (EtG) will also be tabulated for each group.

Data will be analyzed in SAS.

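### The only chart review for 30-day re-admission and ED visits is set for the day the outcome window closes, with no minimum lag or repeat look, so it can miss late events (minor).

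*Combined protocol and SAP*

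**What the plan says.** The Combined protocol and SAP gives the timing of this review three times, each time as 30 days:

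- Section IV.C, Study Design and Research Methods: further data are collected "at SUDS follow up, and 30-days post-discharge by chart review".
- Section IV.C, Data Collection: re-admission comes from a chart review "conducted by research team members at 30-days post-discharge".
- Table 4: the step is labelled "30-day chart review [data collection point #4".

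The outcome window is also 30 days. Table 4 collects admissions and ED visits "within 30 days of discharge date (date, location, up to top 3 main diagnoses based on documentation available", and section IV.F, Data Analysis Plan, states that "all-cause hospital re-admission within 30-days of discharge will be recorded as a binary outcome". ED visits are to be handled in a similar way.

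For sources, the Table 4 instruction begins "Should check encounters tab as well as" and goes on to Care Everywhere for the Denver Metro region. The consent entry in Table 4 notes that "some hospitals require permission" before outside records can be seen.

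No section states a minimum interval between the close of the window and the review, a second look, or how to code a participant whose outside records are incomplete at the review.

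**The concern.** A review on the closing day of the window looks back over a period that may not yet be over, or not yet fully on record. Two kinds of event can be missed: an admission later on day 30 than the review, and an encounter at another hospital in the last days of the window that Care Everywhere does not yet show. An abstractor who finds no encounter has only one natural entry in a binary field, and nothing in the analysis plan provides for another.

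The error runs one way. Looking too early can hide an event but cannot create one, so the recorded re-admission and ED rates can only be too low. This matters for Aim 2, which is to estimate the 30-day re-admission rate. Section IV.F offers the estimates as input to the sample size of a later effectiveness trial. This chart review is the only source specified for both utilization outcomes.

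**Working it through.** **Plan's own figure.** The plan gives no figure for records missed at the review. Its only computed figure for this outcome is power: about 80% with about 60 participants at 25% vs 15%. With 20 per arm and a two-sided 5% test, I get 11.9%, so that figure does not reproduce. That is a separate matter, and nothing below rests on it.

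**Inputs from the documents.** Window of 30 days; re-admission rates of 25% (linkage alone) and 15% (a medication arm); 60 participants.

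**Assumptions, since the documents are silent.**
- Equal allocation, 20 per arm, with both medication arms at 15%.
- Admissions spread evenly over the 30 days.
- Admissions in the last L days are affected, and a share u of them is not visible at the review. I take L from 1 to 7 days and u from 25% to 100%.
- One admission per re-admitted patient, and the same loss in every arm.

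**Formulas.**
- Expected re-admissions: 20 × 0.25 + 40 × 0.15 = 5 + 6 = 11.
- Sensitivity S = 1 − (L/30) × u.
- Recorded rate = true rate × S.
- Expected number missed = 11 × (1 − S).

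| L (days) | u | S | 25% recorded as | 15% recorded as | Difference (points) | Missed among 60 |
|---|---|---|---|---|---|---|
| 1 | 25% | 0.992 | 24.8% | 14.9% | 9.9 | 0.09 |
| 1 | 100% | 0.967 | 24.2% | 14.5% | 9.7 | 0.37 |
| 3 | 50% | 0.950 | 23.8% | 14.3% | 9.5 | 0.55 |
| 3 | 100% | 0.900 | 22.5% | 13.5% | 9.0 | 1.10 |
| 7 | 50% | 0.883 | 22.1% | 13.3% | 8.8 | 1.28 |
| 7 | 100% | 0.767 | 19.2% | 11.5% | 7.7 | 2.57 |

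The last row is extreme: every admission in the final week, including those at Denver Health itself, would have to be invisible on day 30.

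**No posting delay at all.** Only admissions later on day 30 are then at risk. That is at most 1/30 of events, so 25% would be recorded as no lower than 25% × 29/30 = 24.2%.

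**Effect on the comparison.** S multiplies both rates, so the risk ratio stays at 25/15 = 1.67 while the risk difference shrinks from 10 points to between 9.9 and 7.7. Power at 20 per arm moves from 11.9% to between 11.8% and 9.8%.

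**Effect on a future trial.** With a two-sided 5% test and 80% power, 25% vs 15% needs 250 per arm. If both recorded rates were carried forward instead, the requirement would be 253 to 346 per arm over the same range.

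**The case against.** The strongest reply is that 30 days is only a nominal label. Table 4 defines what is collected by encounter date, so an abstraction run some weeks later would still fit the text. That reading is possible, and it softens the point. It does not remove it, because the Data Collection text says when the review is conducted and a look on day 30 would comply fully. If the label is loose, one participant could be reviewed on day 30 and another on day 50, with different capture.

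Several other objections stand and limit the size:

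- No posting delay is documented, either for Care Everywhere or for Denver Health's own encounters tab. The lags above are assumptions, including whether there is any lag.
- A patient re-admitted more than once counts as an event if any one admission is visible, and Table 4 records up to five. The formula therefore overstates the loss for such patients.
- Sampling error is much larger. An observed 5 of 20 has an exact 95% interval of roughly 9% to 49%.

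A reader might also infer stronger things that the documents do not support:

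- **That the plan codes unseen admissions as non-events.** No such rule is written. It is only the likely default of a binary field with no rule for incomplete records.
- **That section IV.E concedes the problem.** It says that "patients may be re-admitted to hospitals that do not show up in our medical record system (Epic", but this is a disclosed gap in network coverage, not a matter of timing. A later review would not cure it.
- **That incomplete diagnoses for a patient still in hospital distort the outcome.** Both utilization outcomes are all-cause, so an admission that is found counts whatever its diagnoses.
- **That the loss favours one arm.** The trial is open-label and masking of the chart abstractor is not described, but nothing shows that timing or visibility would differ by arm.

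**Conclusion.** The point holds as a minor one. As written, the single review for both 30-day utilization outcomes may be done on the day the window closes, and a review at that time can only lose events. Under the stated assumptions the loss is about 0.1 to 2.6 admissions among 60 participants. No single corrected rate can be given, because the documents contain no record-posting time.

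A reader might take this as a serious threat to the treatment comparison. It is not: a loss common to all arms leaves the risk ratio unchanged and hardly moves the power. A loss of nearly a quarter of events needs either the extreme last row of the table or, for example, half of all admissions at outside hospitals with a 14-day delay (0.50 × 14/30 = 23%). The documents give no basis for either. What remains is a small, avoidable downward bias in the rates that Aim 2 sets out to estimate.

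**What to change.** In the Data Collection text and in Table 4, data collection point #4, state that the chart review is done no earlier than a fixed number of days after day 30, the same for every participant. The sponsor should choose that lag from known record-posting times; two weeks, making the earliest review day 44, is an example only. Keep the existing rule that only encounters dated within 30 days of discharge count. Align the timing phrase in the Study Design and Research Methods text.

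The cost is a sentence and a table edit, with no added visit, staff or review. The one downside is that the last participants' outcomes become final a few weeks later.

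### Enhanced linkage is delivered after the arm is known, and no listed data item shows whether intake was finished or an appointment given

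*Combined protocol and SAP*

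**What the plan says.** Section IV.C, under Intervention, defines the shared background: "All groups will receive enhanced linkage to care that includes contingency management, initiation of biopsychosocial intake, and appointment scheduling". Arm 3 is described as "No single-dose medication", so linkage is its only study treatment beyond the standard consultation that every participant has. The Data Analysis Plan (Section IV.F) states that the drug groups "will be compared against the group that received enhanced linkage to care alone".

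Table 4 sets out the patient flow. The screening, consent and randomization step ("Simple randomization by algorithm") records the assigned group. In the next row the ToD counselor collects baseline data, then does the biopsychosocial intake and "sets up SUDS appointment within 1 week of discharge". A note in that row says "Discharge date is not always predictable" and asks the addiction consult service to review participants still in hospital, contact ToD and update the date in REDCap as needed.

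The narrative of Section IV.C gives a different order. There, ToD obtains baseline data after consent, patients are then randomized, and booking runs alongside the arrangements for the intervention: "Meanwhile, a TOD counselor will work to establish a follow-up date within seven days post-discharge". The trial is open label, with 45 to 60 participants planned.

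Table 1 lists follow-up rate among the primary feasibility outcomes. The Data Analysis Plan tallies it overall.

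**The concern.** Comparing each drug arm with linkage alone isolates the drug only if linkage is the same in every arm. Here the intake (in Table 4) and the booking (in both places) come after assignment, and the staff who deliver them are not kept from knowing the arm. Counselors could, without intending to, put more or less effort into one arm. The listed data would not show it among patients for whom baseline data were collected.

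The second problem does not depend on any difference between arms. The pilot is meant to yield lessons for a larger trial, and follow-up at the Substance Use Disorder Services (SUDS) clinic is one of its main readouts. If attendance is poor, the investigators need to know whether patients were given an appointment and did not come, or were never given one. These call for different remedies in the next trial, and the planned data do not separate them.

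**Working it through.** The plan states no figure for linkage delivery, so the check is mainly a comparison of the text.

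**Order of steps**
- Table 4: consent and randomization, then ToD baseline data, then intake and booking, then the intervention.
- Narrative of Section IV.C: consent, then ToD baseline data, then randomization, then booking alongside the intervention.
- The two agree that booking follows randomization. They conflict on baseline data. Only Table 4 places the intake explicitly.

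**What is recorded (Table 4)**
- Point 1: demographics, baseline clinical data, PHQ9, TLFB, SOCRATES-8A and ACE.
- Point 2: vital signs, laboratory values, symptoms, acceptability and readiness to change, some of them by arm.
- Point 3: questionnaires and contingency management feedback, from clinic attenders only.
- Point 4: admissions, ED visits and laboratory results from the chart.
- No point lists intake completed, appointment given or appointment date. The date to be updated in REDCap reads, in context, as the discharge date.

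**What the indirect traces can show**
- Under the Table 4 order, a patient whom ToD never reached would have missing point 1 data and no $10 payment, which is due on completed baseline data. That can be tabulated by arm.
- Baseline data come before intake and booking, so a patient can have complete baseline data and the payment with neither step done.
- Under the narrative order, baseline data precede randomization, so their presence says nothing about the later booking.
- Attendance is the result that linkage aims at. It does not show that linkage was delivered.

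**Follow-up rate: an illustration**

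Inputs: attendance without linkage 2/17 = 11.8% (Section III, matching the figure in Section II), and attendance with linkage 50% (assumed). With d the proportion in whom linkage is delivered:

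attendance = d × 0.50 + (1 − d) × 0.118

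- d = 0.95: 0.475 + 0.006 = 48.1%
- d = 0.85: 0.425 + 0.018 = 44.3%
- d = 0.75: 0.375 + 0.030 = 40.5%

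An observed 40.5% therefore fits 75% delivery of linkage that brings in half of those who get it. It fits equally well full delivery (d = 1) of linkage that brings in only 40.5%. Attendance alone cannot tell these apart.

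**Between-arm difference: an illustration**

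If delivery were 95% in one arm and 85% or 75% in another, attendance would differ by 3.8 or 7.6 points with no drug effect. The sign depends on which arm is better served. In arms of 20 this is 0.8 or 1.5 patients, and the standard error for the first contrast is √(0.481 × 0.519/20 + 0.443 × 0.557/20) = 0.158, about 16 points.

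For re-admission, the spurious difference is (gap in delivery) × (effect of linkage on re-admission). Neither is in the documents. Assumed gaps of 10 to 50 points and effects of 5 to 15 points give 0.10 × 0.05 = 0.5 points up to 0.50 × 0.15 = 7.5 points. The Data Analysis Plan's example difference is 10 points (25% against 15%). At 20 per arm the 95% half-width around it is 1.96 × √(0.25 × 0.75/20 + 0.15 × 0.85/20) = 24.6 points.

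**The case against.** The strongest reply is that this is fidelity tracking in a pilot that makes no claim to robust hypothesis testing. Patients whom the counselor never reached would show as missing baseline data under Table 4. The consult service is told to review participants in hospital, whatever their arm, and to contact ToD. Follow-up is only tallied overall, and any plausible imbalance is small beside sampling error. Holding randomization for a separate team could also lose consented patients and lower recruitment, itself a primary feasibility outcome.

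Much of this stands. It narrows the gap to patients who were reached but whose intake or booking was not finished or was handled differently by arm. It also means that the main use of better records is to interpret the overall follow-up rate. It does not close the gap: the review instruction creates no record of delivery, and the missing-data signal exists only under one of the two stated orders.

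A reader might go further and infer that drug-arm patients stay longer while waiting for a dose, and so receive more linkage. The documents do not support this. Dosing may be on the day of consent and is timed near discharge, and no text says that discharge is held for it. In Table 4 the counselor's step precedes the intervention in every arm. A reader might also infer that linkage leaves no trace at all. The card payment and the feedback item are indirect traces, though neither shows that intake or booking was completed.

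**Conclusion.** The point holds as a gap in sequence and in data capture. Booking follows randomization in both descriptions, intake does so in Table 4, the arm is not withheld from the counselor, and no listed item shows that either step was completed. Unequal or incomplete linkage among patients who were reached could not be detected, and a low follow-up rate could not be interpreted.

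The documents do not establish that any bias exists, which arm it would favour, or how large it would be. The illustrative 4 to 8 points for attendance and 0.5 to 7.5 points for re-admission rest on assumed inputs; only the 11.8% comes from the protocol, and it is 2 patients of 17. The case for acting is that the change is cheap and serves the pilot's own purpose. The primary comparison has not been shown to be compromised.

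**What to change.** 1. Reconcile the narrative of Section IV.C with Table 4. Have ToD collect baseline data, complete the biopsychosocial intake and book a provisional SUDS appointment before the arm is opened. Afterwards, change only the appointment date if discharge moves. The narrative already has ToD see patients before randomization, so this extends an existing contact.
2. Add three REDCap fields for all arms: intake completed (yes/no, with date), appointment given before discharge (yes/no), and appointment date.
3. Report linkage delivery by arm, descriptively, beside the follow-up rate.

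The cost is three fields and an earlier counselor visit, with no additional staff. Some patients will wait for the counselor before randomization, and a few may be lost in that interval; counting patients who consent but are not randomized would show how many. If the reordering proves impractical, the fields alone still make delivery visible, though linkage would then remain open to influence from knowledge of the arm.
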